1. LIST OF ABBREVIATIONS

1.1. HIV Medications (generic name) and corresponding abbreviations

Abbreviation	Medication Name	
3TC	lamivudine	
ABC	abacavir	
ATV	atazanavir	
ATV/c	atazanavir/cobicistat	
ATV/r	atazanavir/ritonvavir	
BIC	bictegravir	
COBI or /c	cobicistat	
DRV	darunavir	
DRV/c	darunavir/cobicistat	
DRV/r	darunavir/ritonavir	
DTG	dolutegravir	
DTG/ABC/3TC	dolutegravir/abacavir/lamivudine	
EFV	efavirenz	
EFV/TDF/FTC	efavirenz/tenofovir disoproxil fumarate/emtricitabine	
EVG	elvitegravir	
EVG/c	elvitegravir/cobicistat	
EVG/c/TDF/FTC	elvitegravir/cobicistat/tenofovir disoproxil fumarate/emtricitabine	
EVG/c/TAF/FTC	elvitegravir/cobicistat/tenofovir alafenamide fumarate/emtricitabine	
EVG/r	elvitegravir/ritonavir	
FTC	emtricitabine	
LPV	lopinavir	
LPV/r	lopinavir/r	
PI/c	cobicistat-boosted protease inhibitor	
PI/r	ritonavir-boosted protease inhibitor	
RAL	raltegravir	
RPV	rilpivirine	
RTV or /r	ritonavir	
TAF	tenofovir alafenamide fumarate	
TDF	tenofovir disoproxil fumarate	
Abbreviation	Class Name	
INSTI	integrase strand transfer inhibitor	
NNRTI	nonnucleoside reverse transcriptase inhibitor	
PI	protease inhibitor	

3. ABSTRACT

Introduction:

Body composition among patients with HIV has evolved over time, from initial manifestations of severe muscle wasting in the pre-antiretroviral therapy (ART) era to observed gains in weight since the introduction of ART. Evidence demonstrates that the body mass index (BMI) of people with HIV is increasing over time. Studies have also observed pronounced increases in weight following ART initiation. Lipodystrophy has been seen primarily with older ART regimens but is still observed with regimens containing newer agents such as protease inhibitors, integrase strand transfer inhibitors, and non-nucleoside reverse transcriptase inhibitors. Apart from irregular body fat deposition, weight gain was previously attributed to an improvement in health, especially among those severely immunocompromised. However, in the current ART era, weight gain has been attributed to the effect of treatment rather than simply an improvement in health with weight gains observed in multiple settings.

Using data from a large population of HIV patients in the US, this analysis will describe weight outcomes among ART-experienced HIV patients using measures of BMI, lipid levels, and diagnoses of lipodystrophy. This analysis will also assess the association between specific core agent initiation and changes in BMI.

Objectives:

Primary:

- Among new users of DTG, RPV, RAL, BIC^{*}, EVG/c, and DRV(/r/c): To describe BMI categories, weight, lipid levels (e.g. total cholesterol, HDL, LDL, triglycerides), and lipodystrophy at core agent initiation and at 6, 12, and 24 months after core agent initiation, stratified by ART- naïve and ARTexperienced.
- Among ART-experienced new users of DTG vs. RPV, RAL, EVG/c, BIC*, or DRV(/r/c): To estimate the association between specific core agent initiation and changes in BMI at 6, 12, and 24 months after core agent initiation.

Secondary:

 Among ART-experienced patients who were suppressed at switch (stable switch) to DTG, RPV, RAL, BIC^{*}, EVG/c, or DRV(/r/c): To describe BMI categories, weight, and lipid panels levels (e.g. total cholesterol, HDL, LDL) at core agent initiation, and at 6, 12, and 24 months after core agent initiation.

*Patients taking BIC will be included for 6-month outcomes only

Study Design:

An observational clinical cohort analysis utilizing prospectively collected electronic medical record (EMR) data obtained from the OPERA® Observational Database will be used to address the study objectives. Subjects will be included from 01AUG2013 through 31DEC2017 and observed through 31DEC2018. HIV-1, ART-experienced patients who are at least 18 years of age and have been prescribed a core agent of interest for the first time will be included.

Endpoints & Outcomes:

- Primary outcomes:
 - o BMI (continuous and categories) and change in BMI (continuous)
 - Weight (continuous) and change in weight (continuous)
 - Total cholesterol, HDL, LDL and triglycerides (continuous and NCEP ATPIII categories)
 - Lipodystrophy diagnoses

4. AMENDMENTS AND UPDATES

Amendment or update no	Date	Section of study protocol	Amendment or update	Reason
<1>	<date></date>	<text></text>	<text></text>	<text></text>
<2>	<date></date>	<text></text>	<text></text>	<text></text>
<n></n>	<date></date>	<text></text>	<text></text>	<text></text>

5. MILESTONES

Milestone	Planned date
Start of data analysis	JAN 2019
End of data analysis	FEB 2019
Preliminary tables	MAR 2019
Final report of study results	APR 2019
Draft abstract	MAY 2019

6. BACKGROUND AND RATIONALE

6.1. Background

Highly active antiretroviral therapy (ART) has changed human immunodeficiency virus (HIV) infection from a fatal illness to a chronic disease [1, 2]. Since the mid-1990's, regimens containing multiple antiretroviral drugs from at least two classes have been the standard of care in HIV treatment [3]. Combination therapy presents multiple barriers to viral replication and limits the development of drug-resistant mutations [3]. Integrase strand transfer inhibitors (INSTI) are the newest tool for prolonging survival and improving quality of life for people with HIV [4]. This class of medications includes raltegravir (RAL), elvitegravir (EVG), dolutegravir (DTG) and bictegravir (BIC). INSTIs appear to result in a more rapid decline in viral load and higher increases in CD4 counts when compared to protease inhibitors (PI) or efavirenz (EFV) based regimens [5-12].

Body composition has been a concern for patients with HIV since the initial manifestations of severe muscle wasting in the pre-ART era [13-16]. However, these concerns have evolved over time as studies have observed increases in weight among people living with HIV since the introduction of ART [17-19]. Lipodystrophy was associated with primarily older ART regimens but is still observed with some regimens containing newer agents including PIs such as darunavir (DRV) or atazanavir (ATV), INSTIs such as RAL, and non-nucleoside reverse transcriptase inhibitors (NNRTI) such as rilpivirine (RPV) [20-23].

Apart from irregular body fat deposition, weight gain was attributed to an improvement in health initially, especially among those severely immunocompromised. More recently, it has been appreciated that obesity and body mass index (BMI) have been increasing in HIV populations over time both before the initiation of ART and after [19]. In a sample of 14,084 patients living with HIV in the North American AIDS Cohort Collaboration on Research and Design (NA-ACCORD), the percentage of patients who were obese at ART initiation increased from 9% to 18% between 1998 and 2010 [17]. In the Swiss HIV Cohort Study, overweight/obesity prevalence increased from 13% in 1990 to 38% in 2012 [24].

In the current ART era, weight gain has been attributed to the effect of the treatment rather than simply an improvement in health with increases in weight following initiation of ART reported in multiple studies [17, 18, 25, 26]. In the NA-ACCORD, 22% of patients with normal BMI at baseline became overweight and 18% of patients who were overweight at baseline became obese after just three years of ART [17]. Out of 1,255 HIV patients enrolled in the U.S. Military Natural History Study between 1985–2004 and followed up to 2007, 62% gained weight after HIV diagnosis, among whom BMI increased by 2.3 kg/m² on average from baseline to last visit (average rate of 0.55 kg/m²) per year). The average weight gain was 7.3 kg with an average rate of 1.71 kg per year [18]. Among 1,600 HIV patients initiating ART in the Swiss HIV Cohort Study, BMI increased on average by 0.92 kg/m² per year (95% CI: 0.83, 1.0) in the first year of ART and 0.31 kg/m² per year (0.29, 0.34) during years 1-4 [24]. Among 1,160 women in the Women's Interagency HIV Study (WIHS), median BMI increases over 5 years were 0.21 kg/m² (90% CI: –1.33, 0.42) for normal baseline BMI, 0.39 kg/m² (90% CI: 0.15, 0.66) for overweight, 0.31 kg/m² (90% CI: -1.18, 0.67) for obese, and -0.36 kg/m² (90% CI: -2.04, 1.08) for morbidly obese women [25]. In the Veterans Aging Cohort Study (VACS), 4,311 ART-naïve patients initiating ART between 2000-2008 gained a median of 2.7 kg (IQR: -1.3 to 7.7) [26].

In addition, duration of ART exposure may also impact weight gain. Between 1999 and 2004 in the Multicenter AIDS Cohort Study (1,059 men living with HIV) and the WIHS cohorts (1,455 women living with HIV), a shorter duration of ART was associated with lower BMI [19]. These studies suggest that both ART initiation in general and time since initiation are associated with increases in BMI and weight [17-19, 25, 26].

To our knowledge, four recent studies have reported on weight or BMI increases associated with specific core agents [27-30]. One cohort study included 462 European patients on DTG for more than six months and observed a significant increase in weight (mean increase: 3 kg) and BMI (mean increase: 1 kg/m²) over follow-up; 20% of the patients experienced >10% increase in weight [28]. However, the follow-up timepoints varied between patients and the study did not include a comparison group. Another cohort study following 495 patients virologically suppressed on EFV/tenofovir disoproxil fumarate (TDF)/emtricitabine (FTC) from the Vanderbilt Comprehensive Care Clinic found that weight change over an 18-month period was highest among patients

switching to an INSTI-containing regimen (2.9 kg) when compared to switching to a PIcontaining regimen (0.7 kg) or continuation with EFV/TDF/FTC (0.9 kg) [27]. The greatest change was observed for patients switching to DTG/abacavir (ABC)/lamivudine (3TC) specifically (5.3 kg) [27]. In the SCOLTA cohort, mean BMI increases were estimated among ART-experienced patients at 6 and 12 months following initiation of a new core agent [29]. Mean BMI increase with DTG (n=225) was 0.18 \pm 0.08 at 6 months and 0.30 \pm 0.10 at 12 months. With RAL (n=382), mean BMI increase was 0.17 \pm 0.07 at 6 months and 0.24 \pm 0.08 at 12 months. With EVG (n=148), mean BMI increase was 0.21 \pm 0.07 at 6 months and 0.23 \pm 0.10 at 12 months. With DRV (n=145), mean BMI increase was 0.32 \pm 0.09 at 6 months and 0.41 \pm 0.10 at 12 months. With RPV (n=218), mean BMI increase was 0.06 \pm 0.07 at 6 months and 0.06 \pm 0.08 at 12 months [29]. Although small, BMI increases from baseline were statistically significant (p<0.05) for all core agents assessed at both 6 and 12 months with the exception of RPV (6 months: p=0.39, 12 months: p=0.51) [29].

In 1,809 ART-naïve patients randomized to ATV/ritonavir (r)/TDF/FTC, DRV/r/TDF/FTC, or RAL/TDF/FTC, weight increased on average by 3.8 kg and BMI by 1.3 kg/m² over 96 weeks [30]. Adjusted logistic regression with multiple imputation was performed to predict severe weight gain (i.e. \geq 10% increase in weight if \geq normal BMI at baseline; \geq overweight at 96 weeks if underweight at baseline) and severe BMI increase (i.e. increase of one or more BMI categories at 96 weeks if \geq normal baseline BMI; \geq overweight at 96 weeks if underweight at baseline). Compared to RAL, patients prescribed ATV/r were less likely to experience a severe weight increase (aOR: 0.72, 95% CI: 0.53, 0.99) and those prescribed DRV/r were less likely to experience a severe BMI increase (aOR: 0.73; 95% CI:0.53, 0.99) [30]. The relative impact on weight gain of most common core ART agents has yet to be determined.

6.2. Rationale

Disentangling weight gain due to improved health status from weight gain due to an undesired effect of therapy requires an assessment of a large number of patients who may be progressing toward a stable health status or in whom a stable health status has been achieved and maintained.

Following raised disproportionality analysis (DPA) scores for both DTG and DTG/ABC/3TC detected through the routine pharmacovigilance, clinical trial data, spontaneous case reports, and published studies were reviewed. The cumulative evidence could not rule out an association between DTG exposure and weight gain, leading to a recommendation for a label change indicating weight gain as an uncommon ADR. This analysis, utilizing data from a large real-world population of treated HIV patients, will provide additional information to support the signal evaluation.

7. **RESEARCH QUESTION AND OBJECTIVE(S)**

Primary:

- Among new users of DTG, RPV, RAL, BIC*, EVG/c and DRV(/r/c): To describe BMI categories, weight, lipid levels (e.g. total cholesterol, HDL, LDL, triglycerides), and lipodystrophy at core agent initiation and at 6,12, and 24 months after core agent initiation, stratified by ART- naïve and ARTexperienced.
- Among ART-experienced new users of DTG vs. RPV, RAL, BIC*, EVG/c or DRV (/r/c): To estimate the association between specific core agent initiation and changes in BMI at 6, 12, and 24 months after core agent initiation.

Secondary:

 Among ART-experienced patients who were suppressed at switch (stable switch) to DTG, RPV, RAL, BIC*, EVG/c, or DRV(/r/c): To describe BMI categories, weight, and lipid panels levels (e.g. total cholesterol, HDL, LDL) at core agent initiation, and at 6,12, and 24 months after core agent initiation

*Due to recent approval and more limited potential follow-up, patients taking BIC will be included for 6-month outcomes only.

8. **RESEARCH METHODS**

8.1. Study Design

Study objectives will be evaluated through an observational analysis of a clinical cohort utilizing prospectively-collected EMR data obtained from the OPERA Observational Database. Study participants will be identified from the most recent database build available.

Period of subject inclusion:

- 01AUG2013 (DTG-approval)
- 31DEC2017

Period of observation:

- 01AUG2013 (DTG-approval)
- 31DEC2018

Population:

- A diagnosis of HIV-1, a positive HIV-1 Western Blot, or a positive HIV-1 enzymelinked immunosorbent assay (ELISA); and a detectable HIV-1 viral load test
- At least 18 years of age at the index date
- Male or female
- Prescribed one of the following core agents as part of a 3-drug regimen for the first time between 01AUG2013 and 31DEC2017:
 - DTG (Tivicay[®], Triumeq[®])
 - RPV (Edurant[®], Complera[®], Odefsey[®])
 - RAL (Isentress[®], Isentress HD[®])
 - EVG/c (Vitekta[®], Stribild[®], Genvoya[®])
 - DRV (/r/c) (Prezista[®], Prezcobix[®], Symtuza[®])
 - BIC (Biktarvy[®])
- Not exposed to >1 core agent of interest concurrently

Index date: The index date for an eligible patient is defined as the first date of the first regimen of interest ever prescribed to a patient after 01AUG2013.

Baseline period: The 12-month baseline period preceding the index date will be used to assess patient demographic and clinical characteristics. Data from the visit closest to the index date will be used for analysis.

Observation period: Patients will be observed from their index date until 6,12, and 24 months post-initiation of the regimen of interest, with the final study end date on 31DEC2018.

Censoring events: (i) End of follow-up (6,12, or 24 months after core agent initiation), (ii) cessation of continuous clinical activity*, (iii) core agent discontinuation, (iv) pregnancy, (v) death, or (vi) study end (31DEC2018).

* Continuous clinical activity is defined as at least one clinic visit within a 12month period. Patients failing to meet the continuous clinical activity requirement will be censored 12 months after their last contact.

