8.2. Study Population and Setting

The analysis population will be identified from the OPERA Observational Database according to the inclusion criteria defined below.

Primary population

1) A diagnosis of HIV-1, a positive HIV-1 Western Blot, or a positive HIV-1specific ELISA; and a detectable HIV-1 viral load test

- 2) At least 18 years of age at the index date
- 3) Male or female patients
- 4) Prescribed DTG, RPV, RAL, BIC, EVG/c and DRV(/r/c) as part of a 3-drug regimen for the first time between 01AUG2013 and 31DEC2017
- 5) Not exposed to >1 core agent of interest concurrently

Subjects with the following criteria will be excluded from the study sample:

- 1) HIV-negative
- A diagnosis of HIV-2, a positive HIV-1/HIV-2 Multispot, a positive HIV-2specific ELISA, a positive HIV-2 Western Blot or a detectable HIV-2 viral load test
- 3) Women who are considered pregnant at the index date
- 4) Transgender patients (potential for weight changes due to hormone use)

Secondary population

The study population for the secondary objectives will be a subset of the primary study population meeting the following additional inclusion criteria:

- Patients switching to DTG, RPV, RAL, BIC, EVG/c or DRV(/r/c) as part of a 3-drug regimen for the first time between 01AUG2013 and 31DEC2017 (excluding ARTnaïve patients)
- Patients with a viral load <200 copies/mL at last viral load test prior to switch to core agent of interest

The descriptive primary objective (1) will be stratified by prior ART exposure (ART-naïve and ART-experienced. The primary objective assessing association between core agent and BMI change (2), and the secondary objective will be restricted to ART-experienced patients. ART-experienced will be defined as history of ART prior to initiation of the core agent of interest, or a baseline viral load of <1000 copies/mL.

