8.3. Variables

8.3.1. Exposure definitions

Exposures

• First exposure to any core agent of interest (DTG vs. RPV, RAL, BIC, EVG/c or DRV(/r/c)), after inclusion in the OPERA database. Prior exposure to other core agents of interest is not allowed after inclusion in the OPERA database.

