Adjusted linear regression models will be used to assess the association between core agent and mean changes in BMI at 6, 12, and 24 months. Baseline variables included in the adjusted model will be selected a priori, based on the literature, including baseline age, sex, race/ethnicity, comorbid conditions and concomitant medications associated with weight gain and weight loss [33, 34], as well as change in viral load and CD4 cell count. Factors associated with the exposure and the outcome identified in the descriptive analyses will be considered for inclusion in the adjusted model if the requirements for confounding are met. Inverse probability-of-censoring weights will be used to account for patients who discontinue treatment or are lost to follow-up and constructed using a logistic regression model.

*This analysis will be stratified by baseline BMI categories (underweight, normal weight, overweight, obese).

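### Starting a second core agent during follow-up is not a censoring event, and the single-core-agent criterion has no stated assessment date and covers only the six agents of interest

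*Protocol*

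**What the plan says.** **Entry.** Section 8.1 admits patients "Prescribed one of the following core agents as part of a 3-drug regimen for the first time between 01AUG2013 and 31DEC2017" and then lists DTG, RPV, RAL, EVG/c, DRV(/r/c) and BIC. It adds the condition "Not exposed to >1 core agent of interest concurrently". Section 8.2 repeats this as inclusion criterion 5. Neither section says when it is assessed or what makes up a 3-drug regimen.

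**Exposure.** Section 8.3.1 states: "Prior exposure to other core agents of interest is not allowed after inclusion in the OPERA database". This looks backward from the index date and is again limited to the six agents.

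**Censoring.** Section 8.1 gives six censoring events: end of the follow-up window, loss of clinical activity, then "iii) core agent discontinuation, (iv) pregnancy, (v) death", and study end. Discontinuation is the only one that concerns treatment.

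**Weights.** Section 8.5.1 says: "Inverse probability-of-censoring weights will be used to account for patients who discontinue treatment or are lost to follow-up". Adding an agent is not mentioned.

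**The concern.** The plan follows patients on treatment: time after the index agent is stopped is censored, and the weights are meant to correct for that. Such an analysis should also say what happens when a patient keeps the index agent and starts another drug of the same kind. The protocol does not. BMI, weight, lipid and lipodystrophy results recorded after the addition would then be credited to the index agent alone.

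This matters most for the second primary objective, the adjusted DTG-versus-comparator difference in BMI change. If the added drug is one of the comparators, the two groups being compared overlap in exposure. If it is an outside agent, the group carries an effect that does not belong to its label. The protocol itself treats outside core agents as relevant to weight: section 6.1 reports an adjusted odds ratio of 0.72 for severe weight increase with ATV/r against RAL, in ART-naïve patients.

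**Working it through.** The plan states no figure on this point, so the first step sets the rules against each possible case.

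| Case | Rule that applies | Result |
|---|---|---|
| Two of the six at index | Criterion 5 | Excluded |
| One of the six + outside core agent + two NRTIs at index | 3-drug requirement | Excluded (four drugs) |
| One of the six + outside core agent + one NRTI at index | None; 3-drug regimen is undefined, and the text does not say whether boosters count | Could qualify and be analysed as the agent of interest alone |
| Index agent later replaced by another | Core agent discontinuation | Censored |
| Index agent kept, outside core agent added later | None | Uncensored under either reading of criterion 5 |
| Index agent kept, another of the six added later | Criterion 5, with no assessment date | Index reading: uncensored. Whole-record reading: excluded on a post-index event |

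The 3-drug condition applies to the initiating prescription and does not operate afterwards. Section 8.1 starts observation at the regimen of interest but censors on the core agent, so a patient can leave the qualifying regimen by addition and remain under observation. The last two rows are the main gap; the third row is the smaller one.

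**Size.** The documents give no frequency of dual use, so every share below is an assumption. The BMI figures are the 12-month mean increases (kg/m²) in the cohort of ART-experienced patients described in section 6.1: DTG 0.30, RAL 0.24, EVG 0.23, DRV 0.41, RPV 0.06.

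*A. Shift in one group's mean* = share with a second core agent × added effect.
- Share assumed: 1% to 10%.
- Added effect: 0.10 (assumed) to 0.35, the widest gap between agents (0.41 − 0.06).
- Smallest: 0.01 × 0.10 = 0.001. Largest: 0.10 × 0.35 = 0.035.

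*B. Shrinkage of a contrast* = D × (1 − p), where a fraction p of the DTG group also takes the comparator and is assumed to show the comparator's mean change.
- D for DTG − RPV: 0.30 − 0.06 = 0.24.
- p = 5%: 0.24 × 0.95 = 0.228, a shift of 0.012.
- p = 15%: 0.24 × 0.85 = 0.204, a shift of 0.036.

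Together the shifts run from about 0.001 to 0.036 kg/m².

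**Scale.** DTG − RAL is 0.30 − 0.24 = 0.06 and DTG − EVG is 0.30 − 0.23 = 0.07. The largest shift under A is a little over half of these (0.035/0.06 = 0.58; 0.035/0.07 = 0.50), but it needs one patient in ten to add a drug with the widest effect in the list. Under B, the DTG − RAL contrast at p = 15% moves by only 0.06 × 0.15 = 0.009.

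**The case against.** Several points against the concern are fair.

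- **Most dual use at entry is already handled.** Two of the six together are barred, the 3-drug rule removes an agent of interest plus an outside agent plus two NRTIs, and replacing the index agent is censored. A reader might infer that patients on two core agents are in general counted as exposed to one. The table above shows otherwise; what remains is additions after index and rare 3-drug combinations. No regimen in appendix 13.1 pairs one of the six with an outside core agent.
- **Criterion 5 sits among the inclusion criteria**, next to age at the index date, so assessment at index is the natural reading. A reader might infer that the plan selects patients on their future treatment. The text permits that reading but does not state it.
- **The objective concerns initiation**, so following patients while they remain on the initiated agent is a recognisable choice, and censoring at additions could itself be informative. This stands as a cost. It does not justify silence, because the plan already censors at discontinuation and proposes weights for it; treating additions in the same way follows the same logic.
- **Coding of additions might be left to the analysis plan.** Operational detail might be. But the protocol itself fixes the eligibility criteria and gives a complete list of censoring events, and that list omits this one.
- **The size is small and its inputs are assumed.** This stands. The shares have no source, and nothing supports the assumption in B that dual users behave like the comparator group. If the effects of two agents added together, the contrast could move either way.

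**Conclusion.** The point holds as a gap in the exposure and censoring rules. With criterion 5 read at the index date, a patient who keeps the index agent and adds any core agent stays uncensored and is analysed under the index agent alone, and the weights do not address this. For an outside agent the gap exists under either reading. For a second agent of interest, the alternative reading replaces contamination with exclusion on post-index information. Two programmers could build different cohorts from the same text. The undefined 3-drug regimen is a minor addition at index.

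The effect is probably small: about 0.001 to 0.036 kg/m² on assumed shares of 1% to 15% and assumed effects. A reader might infer that the DTG contrasts become uninterpretable, or that dilution by a known amount can be expected. The documents support neither, since they do not say how often a second core agent is added. The case for change rests on consistency with the plan's own on-treatment approach and on the low cost.

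**What to change.** 1. In 8.1 and 8.2, state that criterion 5 is assessed at the index date and covers any core agent, not only the six. Say which drugs count as core agents (at least the six plus ATV, EFV and LPV) and that boosters are not counted. This also closes the gap left by the undefined 3-drug regimen.
2. In 8.1, add the start of any additional core agent to the censoring events.
3. In 8.5.1, include that event in the censoring-weight model alongside discontinuation and loss to follow-up.

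These are changes to analysis definitions and do not affect how patients are treated. The work is protocol wording and a re-run of the selection query. The price is slightly more censoring, which may be informative and so has to be weighted, and the loss of a few patients on unusual regimens. Reporting how many patients in each group are censored for this reason would supply the frequency that is now missing.

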8.3.2. Outcomes of Interest

- 1. BMI/weight:
 - Weight (in kg) will be assessed at baseline, and at 6 months, 12 months, and 24 months after core agent initiation
 - BMI will be assessed at baseline, and at 6 months, 12 months, and 24 months after core agent initiation. BMI will be defined as:
 - $BMI = weight/height^2$
 - Weight measured in kg
 - Height measured in m
 - Baseline BMI identified using weight measured within 3 months prior to or on index date
 - BMI categories will be assessed at baseline, and at 6 months, 12 months, and 24 months after core agent initiation (shown in Table 11)
 - Changes in BMI after 6 months, 12 months, and 24 months on the core agent of interest will be calculated as:
 - $\Delta BMI = BMI_n BMI_0$
 - Where BMI_n is BMI at 6, 12, or 24 months and BMI₀ is BMI at baseline
 - Changes in weight after 6 months, 12 months, and 24 months on the core agent of interest will be calculated as:
 - $\Delta Weight = Weight_n Weight_0$

Where Weight_n is weight at 6, 12, or 24 months and Weight₀ is Weight at baseline

- Time windows for BMI and weight
 - BMI/weight at 6 months: BMI measured the closest to 6 months after core agent initiation, between >3 and ≤9 months
 - BMI/weight at 12 months: BMI measured the closest to 12 months after core agent initiation, between >9 and ≤15 months
 - BMI/weight at 24 months: BMI measured the closest to 24 months after core agent initiation, between >21 and ≤27 months
- 2. Total cholesterol/HDL/LDL/triglycerides:

- Lipids (total cholesterol, HDL, LDL, triglycerides) will be assessed at baseline and at 6 months, 12 months, and 24 months after core agent initiation
- Time windows for lipid panels
 - Lipids at 6 months: lipids measured the closest to 6 months after core agent initiation, between >3 and ≤9 months
 - Lipids at 12 months: lipids measured the closest to 12 months after core agent initiation, between >9 and ≤15 months
 - Lipids at 24 months: lipid measured the closest to 24 months after core agent initiation, between >21 and ≤27 months
- Total cholesterol levels¹
 - Normal: < 5.2 mmol/L or <200 mg/dl

 - Borderline Abnormal: ≥ 5.2 to < 6.2 mmol/L or ≥ 200 to < 240 mg/dl
 - Dyslipidemia: ≥ 6.2 to < 7.2 mmol/L or ≥ 240 to < 280 mg/dl
 - Severe dyslipidemia: ≥ 7.2 mmol/L or ≥ 280 mg/dl
- LDL levels¹
 - Normal: < 2.5 mmol/L or <100 mg/dl

 - Borderline Abnormal: ≥ 2.5 to < 3.3 mmol/L or ≥ 100 to < 130 mg/dl
 - Dyslipidemia: ≥ 3.3 to < 4.1 mmol/L or ≥ 130 to < 160 mg/dl

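### BMI change is anchored on one weight near the index date and earlier pre-index weights go unused, so gain in ART-experienced patients cannot be told from continuing trend

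*Protocol*

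**What the plan says.** Protocol 8.1 defines the look-back: "The 12-month baseline period preceding the index date will be used to assess patient demographic and clinical characteristics". It then reduces it to one value: "Data from the visit closest to the index date will be used for analysis". That is the general rule for baseline characteristics, and 8.3.3 repeats it for the covariates.

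BMI has its own rule in 8.3.2: "Baseline BMI identified using weight measured within 3 months prior to or on index date". The outcome is follow-up BMI minus this baseline value, introduced as "Changes in BMI after 6 months, 12 months, and 24 months on the core agent of interest will be calculated as".

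The adjusted model in 8.5.1 names its a priori covariates, "including baseline age, sex, race/ethnicity, comorbid conditions and concomitant medications associated with weight gain and weight loss", "as well as change in viral load and CD4 cell count". Other factors may enter if the descriptive analyses show them to be confounders. The model is stratified by four baseline BMI categories. Continuous baseline BMI is not named as a covariate, and no earlier weight or pre-index weight change appears in 8.3.2, 8.3.3 or 8.5.1.

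The rationale in 6.2 sets the task as "Disentangling weight gain due to improved health status from weight gain due to an undesired effect of therapy".

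**The concern.** Many ART-experienced patients have a weight history before they start the new agent. If they were already gaining, part of the change after the index date would have happened without the switch. The plan includes no group that stays on its previous regimen, so the patients' own earlier trajectory is the only reference inside the study for what would have happened otherwise. The protocol's background shows why such a reference matters: it faults one DTG cohort for having no comparison group, and it cites a switch study in which patients who did not switch still gained weight.

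Two readings are at stake. The within-agent gains (objective 1 in ART-experienced patients, and the stable-switch objective) may be taken as gains associated with the agent when they include trend. The DTG contrasts (objective 2) could be distorted if starters of one agent were already gaining faster than starters of another.

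**Working it through.** The protocol gives no figure for the effect of the baseline anchor, so there is nothing of its own to reproduce on that point. Table 2 is checked in step 5 because it might be used as a yardstick.

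**1. Trend rates quoted in the protocol (6.1).**
- ART initiators: 0.92 kg/m² per year "in the first year of ART and 0.31 kg/m² per year (0.29, 0.34) during years 1-4".
- Women's cohort, median change over 5 years: 0.21 (normal), 0.39 (overweight), 0.31 (obese), -0.36 (morbidly obese). Divided by 5: 0.042, 0.078, 0.062 and -0.072 per year.

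**2. Trend inside the within-agent change.** Formula: yearly slope × years since index.

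| Slope (kg/m²/year) | 6 months | 12 months | 24 months |
|---|---|---|---|
| 0.042 | 0.021 | 0.042 | 0.084 |
| 0.078 | 0.039 | 0.078 | 0.156 |
| 0.31 | 0.155 | 0.31 | 0.62 |

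A baseline weight taken a full 3 months before index adds up to 0.31 × 0.25 = 0.08 at the highest of these slopes.

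For comparison, 6.1 quotes mean 12-month gains in ART-experienced starters of 0.30 (DTG), 0.24 (RAL), 0.23 (EVG), 0.41 (DRV) and 0.06 (RPV). In the cited switch study, patients who stayed on their regimen gained 0.9 kg over 18 months against 2.9 kg after a switch to an INSTI: 0.9 / 2.9 = 0.31 of that gain.

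**3. Trend inside the DTG contrast.** A slope common to all agents cancels. What remains is (difference in pre-index slopes) × (fraction that persists) × (years). The documents give neither of the first two quantities. As an assumption, with full persistence, a difference of 0.1 per year gives 0.05, 0.10 and 0.20 kg/m² at 6, 12 and 24 months. A difference of 0.2 gives 0.10, 0.20 and 0.40. With equal slopes the bias is zero.

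**4. What adjustment removes.** Assume two agents with no drug effect, individual slopes that persist (SD 0.8 per year), measurement SD 0.5, a slope difference of 0.10, and an earlier weight 12 months before index.
- Planned 12-month change: spurious difference 0.10. Adding continuous baseline BMI leaves it at 0.10.
- Adding the earlier weight as a covariate: the coefficient of prior change is about (0.8² − 0.5²) / (0.8² + 2 × 0.5²) = 0.39 / 1.14 = 0.34. The remainder is 0.10 × (1 − 0.34) = 0.066. Simulation with baseline BMI also in the model gives 0.063.
- Comparing agents on post-minus-pre change: about 0.00.

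With a slope difference of 0.20 the simulated values are 0.20, 0.13 and 0.00.

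**5. Table 2.** A noncentral F calculation with 4 exposure degrees of freedom, 14 predictors and alpha 0.05 (assumed; not stated) reproduces all ten rows. For ρ = 0.20 and N = 292, λ = 292 × 0.04 / 0.96 = 12.17. The conversion d = 2ρ / √(1 − ρ²) gives 0.41 there and treats the outcome SD as 1. Table 2 is therefore arithmetically sound, but it describes an overall 4-df test at SD 1 and not a pairwise DTG contrast.

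**The case against.** The strongest reply is that one baseline value nearest to index is conventional, that the descriptive objectives claim only to describe, and that covariate detail can be left to an analysis plan. The adjustment set in 8.5.1 is open. Change in viral load and CD4 count, the restriction to ART-experienced patients, the suppressed stable-switch subset and the baseline BMI strata all address gain from improved health. Year of ART initiation, length of previous regimen and number of prior ART classes are also listed.

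Much of this stands. The nearest-value rule is not an error in itself, and these variables may reduce a slope difference. But none of them measures prior weight change. The route for adding factors runs through the descriptive analyses, which cover the variables in 8.3.2 and 8.3.3. Baseline BMI could enter that way; prior weight change could not, because it is never derived.

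A reader might go further and infer that a trend of 0.31 kg/m² per year explains the quoted gains, or that the DTG contrasts are confounded. The documents do not support either:
- The 0.31 comes from patients starting ART, not from experienced switchers. It sits badly with the women's cohort (at most about 0.08 per year) and with RPV starters, who gained only 0.06 in 12 months.
- A common trend cancels between agents, and nothing in the documents shows that pre-index slopes differ. Persistence is also uncertain, since the prior slope was observed on the regimen being stopped.
- Setting an assumed bias against the differences in Table 2 would overstate the consequence, for the reasons in step 5.

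**Conclusion.** The concern holds in a limited form. For ART-experienced and stable-switch patients, the plan as written cannot separate change after starting an agent from a trend already in progress. On the protocol's own citations, trend could contribute from about 0.04 to 0.31 kg/m² at 12 months; the width of that range is a reason to measure the trend in this cohort. ART-naïve patients have no prior-ART trend and are outside the point.

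For the DTG contrasts the bias is conditional: it needs pre-index slopes that differ between agents, persist after the switch and survive the planned adjustment. Its size is unknown. The 0.10-0.20 kg/m² at 12 months in step 3 only illustrates assumed slope differences. This is a gap to close with a supporting analysis. It does not invalidate the primary comparison or Table 2.

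**What to change.** - **8.3.2 and 8.3.3:** for ART-experienced patients, define an earlier pre-index BMI, for example the value closest to 9 months before index within >6 to ≤12 months.
- **8.5.1 and 8.5.2:** report annualised pre-index BMI change beside annualised post-index change for each agent, with the number of patients who have an earlier weight.
- **8.5.1, main model:** add continuous baseline BMI within the existing strata.
- **8.5.1, sensitivity analysis in patients with an earlier weight:** (a) add the earlier BMI alongside baseline BMI; (b) compare agents on post-minus-pre slope change. Both are needed, because one noisy earlier weight as a covariate removes only part of a slope difference (step 4).

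The cost is protocol wording and some programming. The limitation is coverage. Continuous clinical activity requires only one visit in 12 months (8.1), and a patient can count as experienced on a baseline viral load below 1000 copies/mL without recorded ART history (8.2), so some will have no earlier weight. The two pre-index weights could also lie little more than 3 months apart, which makes individual slopes noisy. The result is a supporting analysis in a subset, and its slope-change form assumes that prior trends would have continued.
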